5 ANALYSIS SETS

The following subject populations will be evaluated and used for presentation and analysis of the data:

- Full Analysis Set (FAS): all randomized subjects;
- Safety Analysis Set (SAF): all randomized subjects who received at least 1 dose of study medication.

The FAS will be analyzed according to randomized treatment while the SAF will be analyzed according to the actual treatment received. The SAF will be the primary population for the analysis of safety endpoints.

5.1 PROTOCOL DEVIATIONS

Any protocol deviation (e.g., wrong inclusion, poor compliance, prohibited concomitant medications, etc.) has been discussed on a case-by-case basis with the clinical team and described in the data review document.

Protocol deviations will be listed for randomized patients, including information on their classification as minor and whether they led to exclusion from any populations and their relation to COVID-19.

6 VARIABLES OF INTEREST

6.1 EFFICACY VARIABLES

6.1.1 Primary efficacy variables

LT4 dose required to maintain TSH in target range (unit: mcg/kg/day)

The LT4 dose is calculated based on the daily LT4 dose (mcg) used in the time period preceding the visit (or the average daily dose on a weekly basis if more than one strength is used over the course of the week) and the body weight (kg) measured during the visit.

6.1.2 Secondary efficacy variables

Laboratory parameters

- Thyroid Stimulating Hormone (TSH);
- Free Thyroxine (FT4);
- Number of events of TSH values above 4.5 mU/L;
- Number of events of FT4 values below the middle of the laboratory normal range

Frequency of dose adjustments

Percent number of subjects (%) who need a dose adjustment in the long-term follow up phase.

Parents' satisfaction questionnaire (PSQ)

The Parents' Satisfaction Questionnaire is completed by the parents/guardian in the eDiary:

at V1 only for infants who are already on TH therapy, and 0-3 days before in-clinic visits for all subjects.

Parents answer questions about the following topics:

- Coping and mental well-being;
- Drug preparation & administration;
- Treatment satisfaction; and
- Medication preference.

The PSQ score at each visit will be computed as sum of all questions scores assigned as reported in Appendix 3.

Caregiver administered Children's Acceptance Tool (CareCAT)

This questionnaire is completed within the eDiary during the first, the third and the eighth week of treatment.

Descriptors:

Swallows well – Medicine is swallowed down

- Observing the act of swallowing the medicine – '[I see that she] drinks the medicine and swallows'
- Ingesting the medicine in absence of negative behaviors – 'He swallows and does not give me a hard time'

Refusal – Resistance of the child (e.g. fighting, crying)

- Defensive behavior preventing the intake of medicine – 'By pushing the spoon' or 'fights with her hands' or 'turns away her head'
- Spitting up – Some medicine is coming out of the mouth immediately
- Forcing the medicine out actively – 'He spits or maybe blows the medicine out'
- Medicine passively leaving the mouth ('overflow' or 'spilling') – 'When the medicines runs down the mouth'

Vomiting – Within 30 minutes after swallowing the medicine the child brings up something [vomits]

- 'She takes out the medicine after feeling nauseous, then vomits it with food'

Medication not taken – No medicine went into the mouth of the child

- No oral intake of medicine – 'She does not want [to take the medicine] until the medicine did not get in [the mouth]'
- Intake without ingesting – 'I have tried to give her but [the medicine] was still not swallowed'

Growth assessments

The following variables about growth are collected: length (cm), weight (Kg) and head circumference (cm).

7 SAFETY AND TOLERABILITY VARIABLES

Signs and symptoms of hypo-/hyper-thyroidism

Total number of subjects experiencing hypothyroidism/hyperthyroidism signs and symptoms.

Physical examination

The following information about abnormalities found during the examination: body system, findings and clinical significance.

Vital signs

Vital signs that will be collected and recorded in the EDC are heart rate and temperature.

7.1 CONCOMITANT MEDICATIONS

All concomitant medications will be coded using World Health Organization Drug Dictionary (WHO-DD) and summarized by Anatomical Therapeutic Chemical (ATC) level 2 and preferred drug name. Concomitant medications will also be listed.

LT4 medications will be summarized by Anatomical Therapeutic Chemical (ATC) level 2 and preferred drug name, separately from the prior and concomitant medications.

7.2 LABORATORY DATA

Only the following laboratory data will be collected:

- Thyroid Stimulating Hormone (TSH);
- Free Thyroxine (FT4); and
- Total Thyroxine (TT4), optional.

Analysis is described under section 6.1.2.

8 HANDLING OF MISSING AND INCOMPLETE DATA

Missing values will not be replaced.

9 STATISTICAL METHODOLOGY

9.1 GENERAL METHODOLOGY

Descriptive statistics

Categorical variables will be summarized by frequency (n) and percentages (%) and quantitative (continuous) variables using measures of central tendency (mean, median) and dispersion (minimum & maximum; 95% confidence intervals; values defining the limits of the 2nd and 3rd quartiles (25th percentile, 75th percentile); and the standard deviation.

P-values and Type I error

All p-value(s) will be rounded to three decimal places. Statistical significance will be declared if the rounded p-value is less than 0.050.

Two-sided 95% confidence intervals (CI) will be calculated.

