#### **General Methods:**

Continuous variables will be summarized using the following descriptive statistics: n (non-missing sample size), mean, standard deviation, median, maximum and minimum. The frequency and percentages (based on the non-missing sample size) of observed levels will be reported for all categorical measures.

Standard statistical tests (chi-square, Cochran-Mantel-Haenszel chi-square, Student's t) will be used to compare Treatment vs. Control. If distributions are severely non-normal, the analyses of continuous variables will be performed on the log-transformed values. If the log transformation does not produce normally distributed data, the Wilcoxon test will be used for comparisons.

All analyses will be conducted using a two-tailed significance level of 0.05 unless otherwise stated. P-values less than or equal to 0.05 will be considered statistically significant. No adjustments for multiple comparisons are planned for exploratory outcomes.

Expected start date:	Estimated date first patient enrolled: September 2021
Expected end date:	Estimated date last patient completed: December 2024

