### **19.3.5 ADJUSTMENT FOR MULTIPLE COMPARISONS**

Not applicable

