3.4 CHANGES FROM STUDY PROTOCOL

Section 19.2 Population for analysis:

The following subject populations were foreseen:

- Full Analysis Set (FAS): all randomized subjects;
- Per Protocol Set (PPS): all randomized subjects with no major protocol deviations; and
- Safety Analysis Set (SAF): all randomized subjects who received at least 1 dose of study medication.

Due to the premature termination of the study and the limited sample size the Per Protocol Set will not be considered for the final analysis.

Section 19.3.1 General Statistical Methods:

Due to the fast changing measurements in the specific population, in relation to growth, the last observation carried forward (LOCF) method will not be used to deal with missing data or in the case of early study discontinuation and missing data will not be replaced.

Section 19.3.2 Efficacy outcomes:

Due to the premature termination of the study and limited sample size all the efficacy analyses will be considered exploratory. LT4 dose/kg, laboratory parameters (TSH and FT4), “Parents’ Satisfaction Questionnaire” will be analyzed with a mixed model adjusted with Kenward-Roger method and considering as first choice the unstructured covariate matrix (other matrixes will be considered if there will be convergence problems). Variables newly diagnosed neonates vs infants already on LT4 therapy and center will not be considered in the models. Normal distribution for LT4 dose/kg, laboratory parameters (TSH and FT4), “Parents’ Satisfaction Questionnaire” will be tested with Shapiro Wilks, if data result not distributed as a normal distribution a log transformation will be applied. LT4 dose/kg, TSH and FT4 levels and Parents’ Satisfaction Questionnaire score at each visit will be compared between treatment groups by Wilcoxon Mann-Whitney test.

Section 19.3.3 Exploratory outcomes:

Time to TSH and FT4 normalization in the neonates will not be evaluated between the treatment groups due to the low number of neonates enrolled (3 randomized to Tirosint-SOL and only 1 to Control).

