9.4 ANALYSIS OF EFFICACY

All efficacy analyses will be considered explorative, due to the low number of subjects enrolled. Efficacy analyses will be performed on Full Analysis Set (FAS).

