9.4.1 Primary efficacy analysis

LT4 dose/kg

The LT4 dose/kg will be calculated based on the daily LT4 dose used in the time period preceding the visit and the body weight measured during the visit. When dosing schedules alternating strengths over the course of the week are used, the daily dose will be calculated as the average daily dose on a weekly basis.

The LT4 dose/kg required to maintain TSH in target range will be analyzed at 12 months of age visit (V8) and when the subject is 2, 4, 6, 9, 15, 18 and 21 months of age (V4, V5, V6, V7, V9, V10, V11) by means of analysis of covariance (mixed model), including treatment group, age at randomization and interactions between visit and treatment group as covariates. Treatment effect at each visit will be estimated.

Normal distribution for LT4 dose/kg will be tested with Shapiro Wilks, if data result not to be distributed as a normal distribution a log transformation will be applied.

The mixed model will be adjusted with Kenward-Roger method and the unconstructed covariance matrix will be used as first choice (other matrixes will be considered if there will be convergence problems).

Summary descriptive statistics will be provided for LT4 dose/kg and results at each visit will be compared between treatment groups by Wilcoxon Mann-Whitney test. This analysis will also be repeated stratified on neonates and infants.

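### The SAP declares statistical significance at 0.050 for every efficacy p-value while calling all efficacy analyses exploratory, so a false significant result is very likely if the two formulations do not differ

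*SAP*

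**What the plan says.** - **Decision rule.** SAP 9.1, under its paragraph on p-values and type I error: "Statistical significance will be declared if the rounded p-value is less than 0.050". No test is exempted. The protocol synopsis states a slightly different threshold: "P-values less than or equal to 0.05 will be considered statistically significant".
- **Status of the analyses.** SAP 3.4: "Due to the premature termination of the study and limited sample size all the efficacy analyses will be considered exploratory". SAP 9.4 repeats it: "All efficacy analyses will be considered explorative, due to the low number of subjects enrolled".
- **Multiplicity.** The SAP has no section on it. Protocol 19.3.5 reads "Not applicable". The protocol synopsis says "No adjustments for multiple comparisons are planned for exploratory outcomes".
- **Primary variable.** SAP 6.1.1 names one, LT4 dose/kg. SAP 6.1.2 lists TSH, FT4, the two event counts, the parents' questionnaire and CareCAT as secondary.
- **Tests on the primary variable.** SAP 9.4.1 fits a mixed model over V4 to V11 and adds "Treatment effect at each visit will be estimated". It then says that "results at each visit will be compared between treatment groups by Wilcoxon Mann-Whitney test", with that comparison repeated within neonates and within infants.
- **Tests on the other endpoints.** SAP 9.4.2 gives TSH and FT4 the same three layers, plus event tests at each visit and in aggregate. The questionnaire gets a model and a Wilcoxon test per visit. CareCAT is tested by day and by week.

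**The concern.** The SAP gives two instructions and does not reconcile them. An exploratory analysis needs no familywise error control, but it then has no basis for declaring significance. SAP 9.1 declares it anyway, for every comparison, and no sentence tells the reader to take the p-values as nominal.

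The primary variable is named but the primary comparison is not. V8 is the age on which the sample size was set, yet SAP 9.4.1 analyses it alongside seven other visits. Two tests address the treatment difference at each visit, and the plan does not say which is the result if they disagree. A report that follows this SAP could announce a significant difference at some visit, on some endpoint, by one of two tests. The reader could not tell that from chance in a trial of 31 children.

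**Working it through.** **1. The plan's own figure.** SAP 3.2 sizes the trial for one two-sided 0.05 t-test of dose/kg at 12 months of age: mean 6, difference 20% × 6 = 1.2 mcg/kg/day, SD 2, allocation 2:1. With 68 and 34 children the noncentrality is (1.2/2) × √(68 × 34/102) = 2.86 and the power is 80.8%, so 102 is reproduced. Dividing by 0.80 for dropout gives 127.5, against the stated 126, which allows 19.0% loss. The error rate behind the design therefore belongs to one test. With 31 children, split 21:10 (assumed), power for the same effect is about 33%.

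**2. Number of tests in SAP 9.4.1 and 9.4.2 for the four main objectives.**

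| Block | Count |
|---|---|
| Dose/kg: 8 visits × 2 tests | 16 |
| TSH and FT4: 2 × 10 visits (V2–V11) × 2 tests | 40 |
| Questionnaire: 8 visits × 2 tests | 16 |
| Wilcoxon repeats in two age strata: (8 + 10 + 10) × 2 | 56 |
| TSH and FT4 events: 2 × (10 visits + 1 aggregate) | 22 |
| CareCAT: 21 days + 3 weeks | 24 |
| **Total** | **174** |

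Not all can reach significance. Protocol Table 2 schedules V4 only for children randomized at 15 days of age or younger, so for at most the 4 neonates (3 vs 1, SAP 3.4). The smallest two-sided exact Wilcoxon p at 3 vs 1 is 2/4 = 0.5. V4 and neonate-only Wilcoxon tests are therefore inert, and about 135 usable tests remain.

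**3. Why independence is the wrong formula.** For k independent tests the chance of at least one p < 0.05 is 1 − 0.95^k, which is 98.3% for k = 80 and 99.8% for k = 120. Here the model and Wilcoxon tests share data, and the visits repeat the same children, so the true figure is lower and has to be simulated.

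**4. Simulation with no treatment effect.**
- From the documents: 31 children, neonates 3:1, visit attendance by protocol Table 2, threshold p < 0.0495 (which rounds to below 0.050).
- Assumed: overall split 21:10, within-child correlation 0.3 to 0.95, correlation between outcomes 0 or 0.5, 8% missed visits, 70% CareCAT diary completion, about 20% non-acceptance. One of the dose/kg runs treated endpoints as independent and used a 30% event rate.
- The mixed model was approximated by per-visit ANCOVA and, separately, by generalised least squares contrasts. The main runs used 1,200 trials per setting.

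| Tests counted | Chance of at least one significant result |
|---|---|
| Dose/kg at V8, model contrast only | about 5% |
| Dose/kg, model contrasts over visits | 20–27% |
| Dose/kg, adding Wilcoxon tests (all children, and infants) | 26–33% |
| Model contrasts only, four outcomes (about 33 tests) | 55–78% |
| Model plus Wilcoxon, four outcomes (about 66 tests) | 64–84% across runs |
| Adding the infant stratum (about 90 tests) | 73–87% |
| Adding event and CareCAT tests (about 135 tests) | 91–96% |

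The four outcomes are dose/kg, TSH, FT4 and the questionnaire. In the last row about 5 of the 135 tests are falsely significant on average. The weekly CareCAT test was simulated ignoring repeated days per child and had a per-test error of about 18%, but it adds only about 2 to 3 percentage points. Removing the Wilcoxon tests would not cure the problem, since model contrasts alone give 55–78%.

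**The case against.** The strongest reply is that the SAP has already dealt with this. It labels all efficacy exploratory in two places, and the synopsis plans no adjustment for exploratory outcomes. Once everything is exploratory, the apparent conflict between the synopsis and protocol 19.3.5 largely disappears. Absence of familywise control is then not in itself an error. That is correct. It does not account for a rule that still declares significance.

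The order of tests is also not wholly absent. The mixed model comes first in each subsection, and for TSH, FT4 and the questionnaire the Wilcoxon comparison is worded as an addition. That suggests precedence but does not state it.

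The percentages rest on inputs that the documents do not supply, and CareCAT, a five-category nominal scale, was simplified to a binary rating. This limits precision at the top of the range. The middle rows do not depend on CareCAT or event rates.

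A reader might go further in three ways that the documents do not support:
- **A false result is near certain.** That needs independent tests, and these are strongly dependent.
- **There are four co-equal primary endpoints, each tested at about ten visits.** Four objectives are listed without ranking, but SAP 6.1.1 names one primary variable. Only TSH and FT4 have ten visits; dose/kg and the questionnaire have eight, and CareCAT uses days and weeks.
- **The added tests were chosen after seeing results.** The SAP history places the per-visit Wilcoxon tests, the stratified repeats and the by-day CareCAT tests in the 2026 revision, after screening had closed. Nothing says that comparative results had been seen.

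**Conclusion.** The point holds, and SAP 9.1 is wrong as written rather than merely short of detail: its declaration rule contradicts the exploratory status given in SAP 3.4 and 9.4. With no treatment effect, at least one significant efficacy result is very likely. The chance is roughly 20–33% for dose/kg alone, about 64–87% for model and Wilcoxon tests on dose, TSH, FT4 and the questionnaire (upper end including the infant stratum), and up to about 96% with event and CareCAT tests. The exact values depend on the assumed arm split, correlations, event rates and diary completion, and on approximations to the mixed model. In every setting tried, the four outcomes together gave a false declaration more often than not. The defect lies in the declaration and the undesignated comparison. It does not lie in the missing multiplicity adjustment.

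**What to change.** - **SAP 9.1:** for efficacy, replace the significance declaration with a statement that all p-values are nominal, unadjusted and descriptive, and that no statistical significance is declared. This also makes the small threshold difference from the protocol synopsis irrelevant for efficacy.
- **SAP 9.4.1 and 9.4.2:** where a mixed model is planned, state that its treatment difference with 95% CI is the reported result at each visit. State that the Wilcoxon test is supportive, and accompany it with a Hodges-Lehmann difference and 95% CI.
- **SAP 9.4.1:** present the V8 (12 months of age) dose/kg difference first, as the main estimate, because the sample size was set on it. It should not carry a significance declaration either: the trial is now wholly exploratory and open-label, with about 33% power for the planned effect.

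**Cost.** Wording, plus the Hodges-Lehmann estimates. No planned test has to be dropped, and SAP 9.1 already provides for two-sided 95% confidence intervals. The sponsor can no longer call individual efficacy results significant. The change makes the results interpretable; it does not restore power.

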9.2 PATIENT DISPOSITION

A complete screening disposition on screened subjects including the number of enrolled subjects, randomized subjects, screening failures and the reasons for screening failure will be provided.

Summary table of not met inclusion and exclusion criteria will also be provided.

A study disposition table on randomized subjects will be provided and it will include number of subjects who completed or discontinued the study and reasons for discontinuation.

Dispositions of randomized subjects who performed each visit and number of patients included in each analysis population will be provided too.

9.3 DEMOGRAPHIC AND SCREENING/BASELINE CHARACTERISTICS

Descriptive statistics of baseline characteristics will be presented for the Full Analysis Set (FAS).

Subjects baseline characteristics will include:

- Demographic data: age at screening, age at randomization, age class (infant or neonates), gestational age, weight at birth, sex, race, ethnicity, length at screening, weight at screening, BMI at screening, head circumference at screening, TSH (mIU/L) and T-4 FREE (pmol/L) levels at CH diagnosis.
- LT4 dose: LT4 dose (mcg/kg/day) at screening (for infants only)
- Hormonal status: TSH (mIU/L) and T-4 FREE (pmol/L) levels at screening (for infants only).
- Vital signs: pulse and temperature at screening.
- Physical examination: abnormal body systems at screening.
- Signs and symptoms of hypo and hyper thyroidism: category (hypothyroidism or hyperthyroidism) and sign or symptom at screening.
- Nutritional intake: breast milk, cow's milk, formula milk, baby food or adult-like food at screening.
- Medical History: those will be summarized by System Organ Class (SOC) and Preferred Term (PT).
- Previous Medications: All previous medications will be summarized by Anatomical Therapeutic Chemical (ATC) level 2 and preferred drug name.

Age at screening, age at randomization, gestational age, weight at birth, length at screening, weight at screening, head circumference at screening, TSH (mIU/L) and T-4 FREE (pmol/L) levels at CH diagnosis, TSH (mIU/L) and T-4 FREE (pmol/L) levels at screening (for infants

only), and LT4 dose (mcg/kg/day) at screening (for infants only) differences between treatment groups will be evaluated using Wilcoxon test.

Sex, ethnicity and race will be compared between treatment groups at each visit using a Chi-squared test or, when the expected values in any of the cells of a contingency table are below 5 or the total number of observations is less than 20, Fisher exact test as appropriate.

The demographic data analysis will be repeated stratified on neonates and infants.

9.4 ANALYSIS OF EFFICACY

All efficacy analyses will be considered explorative, due to the low number of subjects enrolled. Efficacy analyses will be performed on Full Analysis Set (FAS).

9.4.1 Primary efficacy analysis

LT4 dose/kg

The LT4 dose/kg will be calculated based on the daily LT4 dose used in the time period preceding the visit and the body weight measured during the visit. When dosing schedules alternating strengths over the course of the week are used, the daily dose will be calculated as the average daily dose on a weekly basis.

The LT4 dose/kg required to maintain TSH in target range will be analyzed at 12 months of age visit (V8) and when the subject is 2, 4, 6, 9, 15, 18 and 21 months of age (V4, V5, V6, V7, V9, V10, V11) by means of analysis of covariance (mixed model), including treatment group, age at randomization and interactions between visit and treatment group as covariates. Treatment effect at each visit will be estimated.

Normal distribution for LT4 dose/kg will be tested with Shapiro Wilks, if data result not to be distributed as a normal distribution a log transformation will be applied.

The mixed model will be adjusted with Kenward-Roger method and the unconstructed covariance matrix will be used as first choice (other matrixes will be considered if there will be convergence problems).

Summary descriptive statistics will be provided for LT4 dose/kg and results at each visit will be compared between treatment groups by Wilcoxon Mann-Whitney test. This analysis will also be repeated stratified on neonates and infants.

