3.2 SAMPLE SIZE

Subjects were randomized in a 2:1 ratio to Treatment (Tirosint®-SOL) or Control (conventional therapy with LT4 crushed tablets). Considering a mean value of 6 mcg/kg/day of LT4 dose at 12 months of age and a standard deviation of 2 mcg/kg, a sample size of 102 neonates and infants (68 Treatment and 34 Control) will have 80% power to detect a difference of 20% in the LT4 dose between the groups using an independent t-test with a 0.050 two-tailed significance level. To account for a drop-out rate of maximum 20%, 126 neonates and infants will be enrolled in the study (84 Treatment and 42 Control) (Peroni 2013).

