3.3 RANDOMISATION

This study was not blinded, all study staff was aware of the treatment assigned.

All eligible subjects were randomly assigned at Visit 1. Subject randomization was 2:1 (Treatment:Control) and stratified by site through an Integrated Web Response System (IWRS).

Randomization was stratified based on age:

- neonates newly diagnosed ≤ 28 days; and
- infants > 28 days already on therapy with LT4.

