9.4.2 Secondary efficacy analyses

Laboratory parameters (TSH and FT4)

Laboratory parameters (TSH and FT4) will be analysed at each time point by means of analysis of covariance (mixed model), including basal value, treatment group, age at randomization and interactions between visit and treatment group as covariate.

Normal distribution for TSH and FT4 will be tested with Shapiro Wilks, if data result not to be distributed as a normal distribution a log transformation will be applied.

The mixed model will be adjusted with Kenward-Roger method and the unconstructed covariance matrix will be used as first choice (other matrixes will be considered if there will be convergence problems).

Summary descriptive statistics will be provided for each laboratory parameter. TSH and FT4 levels at each visit will also be compared between treatment groups by Wilcoxon Mann-Whitney test. This analysis will also be repeated stratified on neonates and infants.

Laboratory data will also be listed with clinically significant information.

TSH values above 4.5 mU/L

The events of TSH values above 4.5 mU/L will be compared between treatment groups at each visit and aggregate from Visit 2 to the last available visit using a Chi-squared test or, when the expected values in any of the cells of a contingency table are below 5 or the total number of observations is less than 20, Fisher exact test as appropriate.

FT4 values below the middle of the laboratory normal range

The events of FT4 values below the middle of the laboratory normal range will be compared between treatment groups at each visit and aggregate from Visit 2 to the last available visit using a Chi-squared test or, when the expected values in any of the cells of a contingency table are below 5 or the total number of observations is less than 20, Fisher exact test as appropriate.

Parent satisfaction assessed by “Parents’ Satisfaction Questionnaire”

Parent satisfaction assessed by “Parents’ Satisfaction Questionnaire” score at V3, V5, V6, V7, V8, V9, V10, V11 will be analyzed by means of analysis of covariance (mixed model), including treatment age at randomization and interactions between visit and treatment group as covariate.

Normal distribution for Parents’ Satisfaction Questionnaire score will be tested with Shapiro Wilks, if data results not be distributed as a normal distribution a log transformation will be applied.

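### The dose/kg mixed model leaves out the screening LT4 dose/kg held for 27 of the 31 children, and SAP v2.0 drops the neonate/infant stratum from all mixed models

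*SAP*

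**What the plan says.** - **Dose/kg (SAP 9.4.1).** The mixed model is specified as "including treatment group, age at randomization and interactions between visit and treatment group as covariates". No baseline dose appears.
- **Questionnaire (SAP 9.4.2).** The terms are the same: "including treatment age at randomization and interactions between visit and treatment group as covariate". No V1 score appears.
- **TSH and FT4 (SAP 9.4.2).** The model has these terms plus the basal value. The SAP gives no reason for the difference.
- **Baseline data (SAP 9.3).** The baseline table includes "LT4 dose (mcg/kg/day) at screening (for infants only"), and the arms are compared on it with a Wilcoxon test.
- **Randomisation (SAP 3.3).** Allocation was stratified by site, and "Randomization was stratified based on age", split into newly diagnosed neonates up to 28 days and older infants already on LT4.
- **Changes from protocol (SAP 3.4).** "Variables newly diagnosed neonates vs infants already on LT4 therapy and center will not be considered in the models". Protocol 19.3.2 had both terms in its models. It had no baseline term for dose/kg or the questionnaire.
- **Status.** SAP 9.4 calls all efficacy analyses explorative. The dose/kg and TSH/FT4 Wilcoxon comparisons are repeated for neonates and infants separately.

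**The concern.** Infants already on LT4 enter at their current daily dose unless an adjustment is needed (SAP 3). An infant's dose/kg at entry therefore plausibly predicts later dose/kg. If it does, leaving it out has two effects. Residual variance is larger than it need be. A chance imbalance in starting dose between two small arms also carries into the estimated difference, in proportion to the slope of later dose on starting dose. A Wilcoxon test on the baseline table detects an imbalance but does not correct for it; a covariate does. In an exploratory study of 31 children the confidence interval is the main product, so its width matters. The neonate/infant factor was used to allocate treatment, and the usual practice is to carry such a factor into the model.

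**Working it through.** **Inputs from the documents.** SAP 3.2: mean 6 and SD 2 mcg/kg/day, a 20% difference (0.20 × 6 = 1.2 mcg/kg/day), 68:34 evaluable, two-sided 0.05. SAP 3: 31 randomised. SAP 3.4: 4 neonates (3 Tirosint-SOL, 1 control), so 31 − 4 = 27 infants.

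**Assumptions.** Arm totals are not stated; I take 21:10 overall (range 22:9 to 20:11) and 18:9 among infants. The correlation r between screening and on-study dose/kg is not given. The r that matters is what remains after age, since age stays in the model. The calculation is for a single visit.

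**1. The plan's own figure.** SE = 2 × √(1/68 + 1/34) = 0.420. The noncentrality is 1.2/0.420 = 2.86 on 100 df, so power is 80.8%. The stated 80% reproduces.

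**2. The same comparison with 31 children and no baseline.** SE = 2 × √(1/21 + 1/10) = 0.768. With age in the model (28 df), the 95% CI half-width is 1.57 and power for 1.2 is 33% (31% to 34% over the range of splits).

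**3. Adding baseline.** Multiply the SE by √(1 − r²) × √(1 + 1/26). The second factor is the small-sample cost of estimating the slope. One further df is lost.

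| Assumed r | SE | Change in SE | CI half-width | Power for 1.2 | Detectable difference at 80% power |
|---|---|---|---|---|---|
| no baseline | 0.768 | – | 1.57 | 33% | 2.23 |
| 0.2 | 0.767 | none | 1.57 | 33% | 2.23 |
| 0.3 | 0.747 | −3% | 1.53 | 34% | 2.17 |
| 0.5 | 0.678 | −12% | 1.39 | 40% | 1.97 |
| 0.7 | 0.559 | −27% | 1.15 | 54% | 1.63 |

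At r = 0.7, power is 52% with a 22:9 split and 56% with 20:11.

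**4. Allowing for the four neonates without a baseline.** The formula treats all 31 children as having a baseline, so it is slightly generous. I used a least-squares simulation with infants 18:9, neonates 3:1, age retained, a constant fill for the neonates plus the stratum indicator, and no neonate–infant gap. Mean SE moves from 0.767 to 0.756 at r = 0.3 (−1%), from 0.768 to 0.694 at r = 0.5 (−10%) and from 0.773 to 0.593 at r = 0.7 (−23%). At r = 0 it rises from 0.767 to 0.788 (+3%), which is the price if baseline predicts nothing.

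**5. Restoring the stratum alone (same simulation, r = 0).**

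| Neonate–infant gap net of age, mcg/kg/day | Mean SE without stratum | Mean SE with stratum | Change |
|---|---|---|---|
| 0 | 0.767 | 0.773 | +1% |
| 1 | 0.777 | 0.774 | about 0 |
| 2 | 0.803 | 0.778 | −3% |
| 3 | 0.841 | 0.779 | −7% |

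**6. TSH/FT4 slope.** Neonates' V1 laboratory values come from the diagnostic workup (Protocol Table 1 footnote), while infants' values are on treatment. One common slope therefore covers two kinds of baseline. Simulations with assumed median TSH of 100 (neonates) and 3 mIU/L (infants) compared a within-stratum slope with the common one. The SE falls by 0–2% at r = 0.3, 6–8% at r = 0.5 and 17–18% at r = 0.7.

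**7. V1 questionnaire.** Protocol 16.1 lists randomisation, dosing evaluation, dispensing and instruction before the request to complete the questionnaire. The trial is open-label (Protocol 13.3). If the list is followed in order, parents know the allocation when they answer.

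**The case against.** The case against acting is substantial.

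- All efficacy analyses are exploratory, and randomisation means that omitting a baseline does not bias the comparison. This lowers the priority but is no reason to discard recorded information.
- The correlation is unknown. Doses may be adjusted at inclusion and at any time afterwards (Protocol 13.1.2), so strong prediction is an inference. This stands, and the gain can only be given as a range that starts at zero.
- SAP v2.0 is dated 24 March 2026, and enrolment closed on 31 March 2024 with 12-month follow-up. New covariates at this stage of an open-label trial can look chosen after the fact. This also stands, and it is why the change must be dated and the current model kept alongside.
- Site is a randomisation stratum too. With up to 20 sites and 31 children, center effects could cost more degrees of freedom than they return, so leaving center out is defensible.

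A reader might infer more than the documents support:

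- **That v2.0 removed the baseline.** It did not. The protocol's dose/kg and questionnaire models had none either; v2.0 removed the stratum and center.
- **That deleting the stratum loses material precision.** The stratum is a cut of age at 28 days, age remains a covariate, and only four children are neonates.
- **That the V1 questionnaire score is a clean baseline ready to be added.** Given the order in Protocol 16.1 it may already reflect the allocation, and adjusting for such a score can bias the treatment effect.
- **That four neonates spoil the TSH/FT4 adjustment.** This depends on assumed medians and an assumed correlation, and the SAP plans a log transformation if values are non-normal.

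**Conclusion.** The point holds for dose/kg. The model omits a baseline recorded for 27 of 31 children, while the neighbouring TSH/FT4 model uses one. The expected reduction in SE is about 3%, 12% or 27% at r = 0.3, 0.5 or 0.7, or about 1%, 10% or 23% once the four neonates' missing baseline is allowed for. At r of 0.2 or less there is no gain, and at r = 0 a small loss. These figures rest on SD 2 from SAP 3.2, assumed arm splits and an assumed r. Even at r = 0.7 power is only about 54%, so adjustment narrows the interval but does not rescue the comparison.

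Restoring the stratum is justified because it was used to randomise and because it is the indicator needed to keep the neonates in the model. Its own effect on the SE is about +1% to −3% for a gap of 0 to 2 mcg/kg/day. For the questionnaire the omission is real, but adding the V1 score without a check on timing is not supported. The TSH/FT4 slope is a secondary matter, with a gain anywhere from about 0% to 18%.

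**What to change.** 1. In SAP 9.4.1, add screening dose/kg as a covariate, defined as the dose in use before randomisation. The definition matters because the dose can be adjusted at inclusion and Protocol 16.1 lists the dosing evaluation after randomisation.
2. Restore the neonate/infant indicator (1 df) in all mixed models. Keep age and leave center out.
3. Set the four neonates' missing baseline dose to a constant, which the indicator absorbs. Without this they would drop out of the model and the analysis would no longer be on the Full Analysis Set.
4. Use the V1 questionnaire score as a covariate only where records show that it was completed before the allocation was known.
5. Optionally, fit a within-stratum basal slope for TSH/FT4 as a sensitivity analysis.
6. Date the change, give the reason in SAP 3.4, and report the current models as a sensitivity analysis.

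The cost is SAP wording and 1–2 degrees of freedom, with no new data. The downside is a late change to an exploratory analysis, which the documentation and the retained model make visible.
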